- 8. Patients without acceptable evidence of immunity to varicella zoster virus (VZV) at randomization (See Appendix 3 for guidance on acceptable evidence of immunity and requirement for serologic testing).
- 9. Patients who have received any live or live-attenuated vaccines (including for VZV, herpes simplex, or measles) within 1 month before randomization.
- 10. Patients who have received total lymphoid irradiation or bone marrow transplantation.
- 11. Patients with any unstable medical/psychiatric condition, as assessed by the primary treating physician at each site.

- 12. Patients who in the last 6 months experienced any of the following cardiovascular conditions or findings in the screening ECG:
 - Myocardial infarction
 - Unstable angina
 - Stroke
 - Transient ischemic attack
 - Decompensated heart failure requiring hospitalization or Class III/IV heart failure

(Additional monitoring guidelines for patients with any pre-existing cardiovascular conditions are provided in Section 5.5.5.)

- 13. Patients with history or presence of a Mobitz Type II AV block, or a third-degree AV block or sick sinus syndrome, unless patient has a functioning pacemaker.
- 14. Patients with baseline QTc interval >500 msec.
- 15. Patients receiving Class Ia (e.g., ajmaline, disopyramide, procainamide, quinidine) or Class III antiarrhythmic drugs (e.g., amiodarone, bretylium, sotalol, ibutilide, azimilide, dofetilide).
- 16. Patients with severe respiratory disease, pulmonary fibrosis, or Class III or IV chronic obstructive pulmonary disease, or with clinically significant lung pathology on chest x-ray. Patients with controlled asthma are allowed to enter the study.
- 17. Patients with any of the following hepatic conditions:
 - severe hepatic injury (Child-Pugh Class C)
 - total bilirubin greater than 2 times the upper limit of the reference range, unless in context of Gilbert's syndrome
 - conjugated bilirubin greater than 2 times the upper limit of the reference range
 - aspartate aminotransferase (AST) or alanine aminotransferase (ALT) greater than 2 times the upper limit of the reference range
 - alkaline phosphatase (AP) greater than 2 times the upper limit of the reference range
 - gamma glutamyl-transferase (GGT) greater than 2 times the upper limit of the reference range
- 18. Patients with a screening WBC count <3500/mm³ or lymphocyte count <800/mm³.
- 19. Patients with any of the following neurologic/psychiatric disorders:

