6.2 Patient demographics/other baseline characteristics

Demographic data will be collected and recorded in the demography eCRF including date of birth, sex, and race. Multiple sclerosis history and previous MS treatment will be recorded in the MS history and previous MS treatment eCRF pages, respectively. The majority of evaluations (Table 6-1) will be performed at Screening. Only review of inclusion/exclusion criteria, vital signs, ECG, and urine pregnancy test (if applicable) will be repeated at Day 1, (randomization). The baseline laboratory values should be available before randomization (part of assessment of inclusion/exclusion criteria).

The treating physician will ask about relevant diseases of the following organs and organ systems: skin; eyes, ears, nose, throat, head and neck (including the thyroid); lungs; heart; breasts; abdomen; lymph nodes; musculoskeletal (including extremities and spine); genitourinary, gynecological organs; and rectum. History of allergies, in particular with respect to Gd-diethylenetriamine penta-acetic acid (Gd-DTPA) will be queried. Patients will be asked if they have a history of alcohol or drug abuse or a history of psychiatric disorders. Any previous disease or surgeries will also be documented. Medical history should be supplemented by review of the patient's medical chart and/or by documented dialog with the patient's treating physician. The source of information will be recorded in the relevant medical history/current medical conditions eCRF.

Previous MS history (including history of relapses) needs to be documented in the patient's medical chart and/or in documented dialog with the patient's treating physician.

Information relating to MS history will be collected in the study including: date of MS diagnosis, date of MS symptoms, eye history (e.g., optic neuritis or uveitis), MS relapse history (i.e., number of relapses since first MS symptoms and number of relapses that required steroid treatment), and history of medications used to treat MS. These data will be collected and recorded in the MS medical history, ophthalmology screening, and MS treatment eCRFs. Medications used to treat MS may include glatiramer acetate, IM IFN beta-1a, SC IFN beta-1a, IFN beta-1b, natalizumab, azathioprine, methotrexate, or any other medications used as MS treatments.

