6.5.3 Laboratory evaluations

Routine blood samples will be collected as described in Table 6-1 and Table 6-2 and analyzed by the central laboratory. Blood samples taken at the screening visit are to be in the fasting state. Blood samples taken at subsequent visits are recommended to be in the fasting state. Details regarding collection of samples, shipment of samples, reporting of results, laboratory reference ranges, and alerting abnormal values will be supplied to the site before site initiation in a study laboratory manual. The results of the analysis will be made available to each site by the central laboratory, at the earliest, 48 hours after receipt of the samples by the central laboratory.

Investigators will be asked to comment on those abnormalities on the respective laboratory result page, including a notation of the clinical significance of each abnormal finding in the patient's source documents. The laboratory sheets will be filed with the patient's source documents. Abnormal laboratory values should not be recorded on the AE eCRF; however,

any diagnoses (or signs or symptoms if a diagnosis is not possible) associated with the abnormal findings should be recorded on the AE eCRF.

Clinically notable laboratory findings are defined in Appendix 1.

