Appendix 3: Guidance on safety monitoring

Patients whose blood pressure reading is \geq 140 (systolic) and/or \geq 90 mm Hg (diastolic) should have their blood pressure retested after 15 minutes of rest. If the blood pressure is still elevated, they should be followed up in one month by an unscheduled visit if the scheduled visit is not due. Should systolic BP \geq 140 and/or diastolic BP \geq 90 mm Hg values be confirmed at the second visit, the patient should be referred to his primary care physician, an independent internist or to the specialty hypertension clinic for evaluation, diagnosis and treatment of hypertension.

Patients with BP values of >160/100 mm Hg (confirmed by repeat testing) at any visit during the study should be immediately referred as above for evaluation, diagnosis and treatment of hypertension.

Newly diagnosed hypertension as well as an aggravation of a preexisting condition must be reported as an AE and appropriate antihypertensive medication/dosage adjustment must be considered by the investigator.

Guidance on monitoring of patients with elevated liver function tests

In case of detection of elevated ALT/AST values >2 and <5 times the ULN range, additional blood chemistry panel including ALT, AST, AP, GGT, total and conjugated bilirubin, albumin may be performed at the investigator's discretion.

If ALT/AST values reach 5 times the ULN, confirmed upon repeat testing within two weeks of the initial result or sooner at the discretion of the investigator, the study drug must be permanently discontinued. Patients who develop symptoms suggestive of hepatic dysfunction such as unexplained vomiting or jaundice, should have liver enzymes checked and fingolimod should be discontinued if significant liver injury is confirmed.

In case of isolated elevation of bilirubin over 2.0 mg/dl (34.2 umol/L) unless in context of Gilbert's syndrome, confirmed upon repeat testing within two weeks of the initial result, the investigator must discontinue the study drug. Additional evaluations may be performed at the discretion of the investigator.

For any unscheduled laboratory assessments performed locally, an identical sample should also be sent to the central laboratory for analysis and capture in the central database.

An interruption or discontinuation of the study drug should be clearly documented and reflected on Dosage Administration Record CRF. AE/SAEs need to be filed as appropriate.

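### If the laboratory's upper limit of normal for total bilirubin exceeds 1.0 mg/dL, exclusion 17 admits values at which Appendix 3 already requires study drug to stop

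*Protocol*

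**What the plan says.** **Entry.** Protocol Section 4.2, criterion 17, sets its laboratory limits as multiples of the ULN. For total bilirubin the exclusion is "total bilirubin greater than 2 times the upper limit of the reference range, unless in context of Gilbert's syndrome". A separate line excludes "conjugated bilirubin greater than 2 times the upper limit of the reference range", and another excludes "aspartate aminotransferase (AST) or alanine aminotransferase (ALT) greater than 2 times the upper limit of the reference range".

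**Stopping.** Protocol Appendix 3, in the guidance on elevated liver function tests, uses a fixed concentration for bilirubin: "In case of isolated elevation of bilirubin over 2.0 mg/dl (34.2 umol/L) unless in context of Gilbert's syndrome". A second test inside two weeks has to confirm the value. The consequence is that "the investigator must discontinue the study drug". The rule does not mention the baseline value. For ALT and AST the same guidance puts the permanent stop at 5 x ULN.

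**Reference range.** Neither document states the ULN for total bilirubin. Protocol Section 6.5.3 says that "laboratory reference ranges, and alerting abnormal values will be supplied to the site before site initiation in a study laboratory manual".

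**Timing.** Table 6-1 schedules chemistry at Screening and next at Month 1. Section 6.2 confirms that no chemistry is drawn at randomisation: "Only review of inclusion/exclusion criteria, vital signs, ECG, and urine pregnancy test (if applicable) will be repeated at Day 1". Screening results must be in hand before randomisation.

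**The concern.** The two bilirubin limits are on different scales, and no section links them. Whether they are compatible depends on a number that is outside both documents. If the ULN is high enough, the protocol admits a patient at a bilirubin that it also treats as a mandatory reason to stop drug. Because the stopping rule has no change-from-baseline condition, nothing needs to happen on treatment for it to apply.

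Such a patient would start study drug (in the fingolimod arms, with first-dose cardiac monitoring) and have to stop once the Month 1 value was confirmed. The discontinuation would reflect the patient's state at entry and not the drug, yet it would be counted in that arm's disposition. A site that kept the patient on drug would breach a mandatory rule, and Protocol Section 11 allows no authorised deviations.

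**Working it through.** The plan gives no figure to reproduce here. The check compares two thresholds.

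**Inputs**
- Entry ceiling: 2 x ULN, that value itself being eligible (Protocol 4.2, criterion 17).
- Stop: bilirubin over 2.0 mg/dL, or 34.2 umol/L (Protocol Appendix 3). I read this as total bilirubin, because Appendix 1 uses the same 2.0 mg/dL and 34.2 umol/L for its total bilirubin notable value.
- Unit factor from the protocol's own pair: 34.2 / 2.0 = 17.1 umol/L per mg/dL.
- ULN: not given. Assumed range 0.9 to 1.5 mg/dL.

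**Formulas**
- Break-even ULN: 2 x ULN = 2.0, so ULN = 1.0 mg/dL (17.1 umol/L).
- Width of the eligible-but-must-stop band: max(0, 2 x ULN - 2.0).
- Stop in ULN units: 2.0 / ULN.

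| Assumed ULN (mg/dL) | Entry ceiling (mg/dL) | Band above 2.0 (mg/dL) | Stop as multiple of ULN |
|---|---|---|---|
| 0.9 | 1.8 | 0 | 2.22 |
| 1.0 | 2.0 | 0 | 2.00 |
| 1.1 | 2.2 | 0.2 | 1.82 |
| 1.2 | 2.4 | 0.4 | 1.67 |
| 1.3 | 2.6 | 0.6 | 1.54 |
| 1.4 | 2.8 | 0.8 | 1.43 |
| 1.5 | 3.0 | 1.0 | 1.33 |

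At a ULN of 1.0 the limits meet without overlapping: exactly 2.0 mg/dL is eligible and is not over the stop. Below 1.0 the entry ceiling lies under the stop. Overlap begins only above 1.0.

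**Other limits that might close the gap.** The conjugated-bilirubin exclusion does not cap total bilirubin in mg/dL. The Gilbert's exemption appears in both rules, so it narrows the affected group without removing the overlap.

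**Comparison within the protocol.** For ALT and AST both limits are in ULN units, with entry at 2 x and stop at 5 x. The margin is 3 x ULN whatever the reference range. Bilirubin has no such assured margin.

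**Where a forced stop would show.**
- Primary analysis: relapses count on or off drug, and patients who stop drug stay in the study (Protocol 5.5.10 and 9.4.3; SAP 4.2.1.3). The patient's relapses and follow-up time are still used.
- Per-protocol analysis: relapses after the stop are dropped and the offset becomes time on drug (SAP 4.2.1.2, supportive analysis 3).
- Disposition: the stop is counted as a premature study drug discontinuation with its reason (SAP 3.2).

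**The case against.** The strongest objection is that the conflict is hypothetical. It needs a ULN above 1.0 mg/dL, and the laboratory manual that would settle this is not available here. That stands, so the point can only be made conditionally. A reader might infer from the two rules that patients certainly can qualify and then be stopped at an unchanged value. The documents do not support that, because at a ULN of 1.0 mg/dL or below it cannot happen.

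The affected group is also narrow. The patient must be without Gilbert's syndrome and must have conjugated bilirubin, AST, ALT, alkaline phosphatase and GGT all within 2 x ULN. The elevation must be isolated, persist on treatment and be confirmed. This too stands. The documents contain nothing from which to estimate how many patients this is.

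A reader might go on to infer a false liver signal or a distorted primary result. Neither follows:
- Protocol 7.1 treats a pre-existing condition as an adverse event only if it worsens, and 6.5.3 keeps bare laboratory values off the adverse event form.
- One SAP 8.2.3 summary counts newly occurring or worsening notable abnormalities, which an unchanged value is not. The by-visit notable counts would include it.
- For the primary ARR, off-drug follow-up is the planned handling.

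The value would also be known before dosing, since screening results are reviewed for eligibility. That review applies criterion 17, however, and criterion 17 passes the patient.

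Finally, a relative entry limit and an absolute stop are not contradictory in themselves. That is correct. The defect is that nothing ensures the first lies at or below the second.

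**Conclusion.** The point holds in conditional form, as a low-priority improvement. The entry and stopping limits for total bilirubin are on different scales, are not reconciled, and the stop ignores baseline. If the laboratory ULN exceeds 1.0 mg/dL, values between 2.0 mg/dL and 2 x ULN are eligible and yet meet the mandatory stop without any change. For ULNs of 1.1 to 1.3 mg/dL, which are assumptions, the band is 0.2 to 0.6 mg/dL wide. If the ULN is 1.0 mg/dL or below, there is no conflict.

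Few patients would be affected; the number cannot be derived from the documents. The consequences are avoidable exposure, discontinuations that reflect a baseline value, and on-drug time lost from the per-protocol analysis. The effect on the primary ARR is negligible. Nothing here says which bilirubin limit is right.

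**What to change.** Reconcile criterion 17 in Protocol Section 4.2 with the bilirubin rule in Appendix 3. Express both limits on one scale, so that no patient who meets the entry limit already meets the mandatory stop at an unchanged value. Stating the laboratory ULN in the protocol would show whether any overlap exists. Which limit applies is for the sponsor's clinical team.

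The cost is one line of wording in one of the two places, and then either a few more screening failures or a restated stopping threshold.

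SAP Section 10 already gives a final count of 1064 randomised patients. The sponsor can therefore also count those without Gilbert's syndrome who had a baseline total bilirubin over 2.0 mg/dL and stopped under this rule. A count of zero would settle the practical impact.

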5.1 Investigational and control treatment

Investigational drug

- Fingolimod (FTY720) 0.5 mg capsules for oral administration once daily
- Fingolimod (FTY720) 0.25 mg capsules for oral administration once daily

Both strengths of fingolimod capsule will be identical in appearance and will be packaged in identical bottles. Medication labels will comply with the legal requirements of each country and be printed in the local language. The medication labels will supply the medication number and information on storage conditions.

Control drug

• Glatiramer acetate 20 mg SC injection once daily.

The medication labels will supply information on storage conditions.

5.2 Treatment arms

There are 3 treatment arms. In the study, patients will be randomized to fingolimod 0.5 mg, fingolimod 0.25 mg, or glatiramer acetate 20 mg (for details about the randomization, see Section 9.6 – Sample size calculation).

5.3 Treatment assignment

At the Randomization Visit, all eligible patients will be randomized via interactive voice response system (IVRS) to 1 of the three treatment arms. The investigator, who is usually the treating physician or his /her delegate, will contact the IVRS after confirming that the patient fulfills all the inclusion/exclusion criteria. The IVRS will assign a randomization number to the patient, which will be used to link the patient to a treatment arm and will specify a unique medication number for the first package of study drug to be dispensed to the patient. The randomization number will not be communicated to the caller.

The randomization numbers will be generated using the following procedure to ensure that treatment assignment is unbiased and concealed from patients and investigator staff. A patient randomization list will be produced by the IVRS provider using a validated system that automates the random assignment of patient numbers to randomization numbers. These randomization numbers are linked to the different treatment arms, which in turn are linked to medication numbers. A separate medication list will be produced by or under the responsibility of using a validated system that automates the random assignment of medication numbers to study drug packs containing each of the study drugs.

The randomization scheme for patients will be reviewed and approved by Biostatistics randomization team.

5.4 Treatment blinding

In order to maintain rater-blinding, all efficacy assessments will be obtained by an Independent Evaluating Physician who must not otherwise be involved with any aspects of patient care and management. Patient care and management and other aspects of the conduct of the study at the study site will be under the responsibility of the Treating Physician.

The independent evaluating physician will remain blinded until the database lock and data analysis has been completed. In order to maintain rater-blinding, all patients will be instructed to wear appropriate clothing to completely cover typical or actual injection sites before all scheduled visits and relapse-related neurologic examinations, and not to discuss their treatment or AEs (e.g., injection site reactions) with the independent evaluating physician. These instructions will also be included on the appointment reminder cards. This procedure is essential to maintain the blinding of the efficacy assessments during the study. The treating physician and all other study staff should not discuss study treatment or AEs with the independent evaluating physician in order to maintain the "rater blind."

All patients receiving injections will be known to the treating physician to be in the glatiramer acetate treatment arm, therefore, only patients receiving oral study drug will require first dose safety monitoring visit to be performed by the treating physician.

To maintain blinding of treatment assignment, all patients will receive the same cooling bag to carry study drug.

Because of the extended duration of first-dose monitoring of patients receiving fingolimod, it is recommended that first-dose monitoring is performed, as far as possible, in a manner that prevents blinded site personnel from becoming aware of the duration of the monitoring period.

In order to maintain the blind for Novartis staff, manual review of data listings that could potentially unblind personnel will be performed by reviewers who are independent of the study team.

5.5 Treating the patient

5.5.1 Patient numbering

Each patient is uniquely identified in the study by a combination of his/her center number and patient number. The center number is assigned by Novartis to the investigative site. Upon signing the informed consent form, the patient is assigned a patient number by the investigator. At each site, the first patient is assigned patient number 1, and subsequent patients are assigned consecutive numbers (e.g., the second patient is assigned patient number 2, the third patient is assigned patient number 3). The investigator or his/her staff will contact the IVRS and provide the requested identifying information for the patient to register them into the IVRS. Only the assigned patient ID will be uploaded automatically in the database. Once assigned to a patient, the patient number will not be reused. If the patient fails to be randomized for any reason, the IVRS must be notified as far as possible within 2 days that the patient was not randomly assigned. The reason for not being randomized will be entered on the screening log, and the demography eCRF should also be completed.

5.5.2 Dispensing the study treatment

Each study site will be supplied with study drug for each treatment arm. One component of the packaging has a 2-part label.

For fingolimod, each part of the label contains a medication number. At all drug dispensation visits, investigator staff will identify the fingolimod study drug package to dispense to the patient by calling the IVRS and obtaining the medication number.

In countries where the label contains a medication number, site staff will identify the glatiramer acetate study drug package to dispense to the patient by calling the IVRS and obtaining the medication number. In countries where the glatiramer acetate label does not contain a medication number, glatiramer acetate will be dispensed from bulk stock at the site. The IVRS will still be involved in tracking dispensation of glatiramer acetate study drug.

Immediately before dispensing the package to the patient, investigator staff will detach the outer part of the label from the packaging and affix it to the source document (drug label form) containing that patient's unique patient number.

5.5.3 Supply, storage, and tracking of study treatment

Study treatment must be received by a designated person at the study site, handled and stored safely and properly, and kept in a secured location to which only the investigator and designated assistants have access. Upon receipt, all study drugs should be stored refrigerated according to the instructions specified on the drug labels. Clinical supplies are to be dispensed only in accordance with the protocol.

Medication labels will be in the local language and will comply with the legal requirements of each country. They will include storage conditions for the drug but no information about the patient except for the medication number.

The investigator must maintain an accurate record of the shipment and dispensing of study drug in a drug accountability ledger. Monitoring of drug accountability will be performed by the field monitor during site visits and at the completion of the trial. Patients will be asked to return all unused study drug and packaging at the end of the study or at the time of study drug discontinuation.

At the conclusion of the study, and as appropriate during the course of the study, the investigator will return all used and unused study drug, packaging, drug labels, and a copy of the completed drug accountability ledger to the monitor or to the address provided in the investigator folder at each site.

Blinded study drug (fingolimod) and glatiramer acetate will be provided to the study centers; no study drug will need to be purchased locally. Fingolimod and glatiramer acetate should be stored in a limited-access area, according to the instructions on the study drug label.

